### **9.3.1.2 Primary Analysis**

The primary analysis of the primary estimand will be a within-group comparison in any VX-548 dose group.

The weekly average of daily pain intensity on an NPRS (hereafter referred to as “weekly average of NPRS”) will be calculated as the average of the non-missing NPRS scores at the baseline and in each week during the treatment period as defined in Appendix A. The baseline score will be calculated if there are at least 4 non-missing NPRS scores during Days -7 to -1. The Week 1 to Week 12 scores will be calculated if there are at least 3 non-missing NPRS scores in each week. The NPRS scores collected up to treatment discontinuation will be used in the calculation of the weekly average of NPRS.

The primary efficacy analysis will be based on a mixed-effects model for repeated measures (MMRM), with change from baseline in weekly average of NPRS at each week as the dependent variable; and fixed effects of treatment group, week (categorical), treatment group-by-week interaction, baseline weekly average of NPRS, baseline weekly average of NPRS-by-week interaction. The model will be estimated using restricted maximum likelihood. The Kenward-Roger approximation will be used to estimate denominator degrees of freedom and adjust standard errors (SE). An unstructured co(variance) structure will be used to model the within-subject errors. If there is a convergence issue, then a compound symmetric covariance matrix will be used to model the within-subject errors. The least squares (LS) mean change from baseline at Week 12 for each treatment group will be presented with the corresponding SE, 95% CI and P-value.

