12.3.3.1 Analysis of Primary Endpoint

The primary efficacy endpoint is the change from baseline in the weekly average of the daily pain intensity on an NPRS at Week 12. The primary analysis will be a within-group comparison in any VX-548 dose group.

The primary efficacy analysis will be based on a mixed-effects model for repeated measures (MMRM), with change from baseline in weekly average of daily pain intensity score as the dependent variable; and fixed effects of treatment group, time (categorical), treatment group-by-time interaction, baseline weekly average of daily pain intensity, baseline weekly average of daily pain intensity-by-time interaction. The least squares (LS) mean change from baseline at Week 12 for each group will be presented with the corresponding SE and the corresponding 95% CI and *P* value.

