12.3.3.2 Analysis of Secondary Efficacy Endpoints

The proportion of subjects with \geq 30% reduction from baseline in the weekly average of daily pain intensity on the NPRS at Week 12 will be summarized descriptively by treatment group and analyzed using the Cochran-Mantel-Haenszel test (stratified by sex and BMI). The proportion of subjects with \geq 50% and \geq 70% reduction from baseline will be analyzed similarly.

The proportion of subjects categorized as much improved or very much improved at Week 12 on the PGIC assessment will be summarized descriptively by treatment group and analyzed using the Cochran-Mantel-Haenszel test (stratified by sex and BMI).

The change from baseline in the weekly average of the DSIS at Week 12 will be analyzed similarly to the primary endpoint.

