**Figure 7-1 VX21-548-103 Study Design**

N: number of subjects

a At the end of the Treatment Period (Week 12), subjects will taper off capsule (pregabalin reference or matched placebo) study drug for 7 days.

A total of approximately 175 subjects will be randomized 2:2:1:2 to 4 treatment arms: VX-548 (high, mid, or low dose) or pregabalin (reference arm) (Table 7-1). Randomization will be stratified by sex (female and male) and body mass index ( $\geq 30$  and  $< 30$  kg/m^2). To maintain the blind, all subjects will receive the same number of tablets once daily (qd) in the morning and the same number of capsules 3 times per day in a double-dummy design. After the Treatment Period, subjects will taper off capsule (pregabalin reference or matched placebo) study drug for 7 days (4 days of dosing every 12 hours, then 3 days of dosing qd), and the Safety Follow-up Visit will occur an additional 7 ( $\pm 2$ ) days later.

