### **9.2.2 Demographics and Baseline Characteristics**

Demographics and baseline characteristics will be summarized based on the FAS by treatment group and overall.

Demographic data will include the following:

- Age at screening (in years)
- Age at screening category ( $\geq 18$  to  $< 65$ ,  $\geq 65$ )
- Sex (male, female)
- Ethnicity (Hispanic or Latino, not Hispanic or Latino, and not collected per local regulations)
- Race (White, Black or African American, Asian, American Indian or Alaska Native, Native Hawaiian or Other Pacific Islander, not collected per local regulations, Other and Multiracial [if 2 or more races reported from a subject])

Baseline characteristics will include the following:

- Weight (kg)
- Height (cm)
- BMI ( $\text{kg}/\text{m}^2$ )
- BMI category ( $\geq 30$  and  $< 30 \text{ kg}/\text{m}^2$ )
- Baseline HbA1c (%)
- Baseline HbA1c category ( $< 7$  and  $\geq 7\%$ )
- Baseline weekly average of NPRS
- Baseline weekly average of NPRS category ( $< 8$ ,  $\geq 8$ )
- Baseline weekly average of DSIS
- Baseline NPSI total score
- Baseline SF-36 physical component summary score
- Baseline SF-36 mental component summary score
- Baseline SF-MPQ-2 total score

- Baseline BDI-2 total score

The scoring of NPSI, SF-36, SF-MPQ-2 and BDI-2 are included in Appendix B.

In addition to demographic data and baseline characteristics, data listings will also be provided for:

- Informed consent
- Inclusion/exclusion criteria violation for subjects with any such violations

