### **9.3.2 Analysis of Secondary Efficacy Variables**

Change from baseline in the weekly average of the DSIS at Week 12: The change from baseline in the weekly average of DSIS at Week 12 will be analyzed similarly to the primary analysis as specified in Section 9.3.1.2. The model will include the change from baseline in weekly average of DSIS scores as the dependent variable; and fixed effects of treatment group, time (categorical), treatment group-by-time interaction, baseline weekly average of DSIS, baseline weekly average of DSIS-by-time interaction. The LS mean change from baseline at Week 12 for each treatment group will be presented with the corresponding SE and 95% CI. In addition, the LS mean change from baseline at each week will also be presented together with the corresponding SE and 95% CI by treatment group. The LS mean

change from baseline and SE at each week will also be presented in figure by treatment group.

The weekly average of DSIS will be calculated by averaging the non-missing DSIS scores at the baseline and in each week during the treatment period as defined in Appendix A. They will be calculated if there are at least 3 non-missing DSIS scores for each week, including the baseline. The DSIS scores collected up to treatment discontinuation will be used in the calculation of the weekly average of DSIS.

[figure not shown]
Proportion of subjects with  $\geq 30\%$ ,  $\geq 50\%$ , and  $\geq 70\%$  reduction from baseline in the weekly average of daily pain intensity on the NPRS at Week 12:

The percentage reduction in the weekly average of NPRS at Week 12 will be calculated as  $100\% \times (\text{weekly average at baseline} - \text{weekly average at Week 12}) / \text{weekly average at baseline}$ . The weekly average at baseline and at Week 12 are the scores used for the primary analysis.

Subjects with  $\geq 30\%$  reduction from baseline at Week 12 will be defined as “responders”. Subjects with  $<30\%$  reduction from baseline at Week 12 or subjects who discontinued treatment early will be defined as “non-responders”. Subjects who complete treatment but have missing weekly average at Week 12 will have the data imputed based on the last available weekly average and their response status will be determined based on the imputed score. The proportion of subjects with  $\geq 30\%$  reduction from baseline in the weekly average of NPRS at Week 12 will be summarized descriptively by treatment group.

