The proportion of subjects with  $\geq 50\%$  and  $\geq 70\%$  reduction from baseline will be defined and summarized similarly.

Proportion of subjects categorized as much improved or very much improved at Week 12 on the PGIC assessment: The proportion of subjects categorized as much improved or very much improved at Week 12 on the PGIC assessment will be summarized descriptively by treatment group. Subjects who complete treatment but have missing data at Week 12 will have the data imputed from the last available measurement. Subjects who discontinue treatment will be considered as “non-responders”.

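### The NPRS and DSIS repeated-measures models leave out the sex and BMI randomisation strata: a small missed improvement that mainly leaves the reported intervals slightly too wide

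*SAP*

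**What the plan says.** **Design.** SAP 7.1 states: "Randomization will be stratified by sex (female and male) and body mass index", with BMI split at 30 kg/m². Protocol 9.1 and the synopsis stratify by the same two factors.

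**Continuous endpoints.** The NPRS model in SAP 9.3.1.2 has "fixed effects of treatment group, week (categorical), treatment group-by-week interaction, baseline weekly average of NPRS, baseline weekly average of NPRS-by-week interaction". Protocol 12.3.3.1 gives the same list, starting with "fixed effects of treatment group, time (categorical), treatment group-by-time interaction, baseline weekly average of daily pain intensity" and adding the baseline-by-time term. The DSIS model in SAP 9.3.2 has "fixed effects of treatment group, time (categorical), treatment group-by-time interaction, baseline weekly average of DSIS, baseline weekly average of DSIS-by-time interaction". None has a term for sex or BMI. The primary analysis is a within-group change from baseline for each VX-548 dose. SAP 7.2 says the study is not powered for comparisons with pregabalin.

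**Binary endpoints.** Protocol 12.3.3.2 has the 30% responder and PGIC proportions summarised and also "analyzed using the Cochran-Mantel-Haenszel test (stratified by sex and BMI"), with the 50% and 70% thresholds handled the same way. In SAP 9.3.2 the 30% responder proportion "in the weekly average of NPRS at Week 12 will be summarized descriptively by treatment group". For 50% and 70%, the proportion with that "reduction from baseline will be defined and summarized similarly". PGIC is likewise descriptive. No Cochran-Mantel-Haenszel test appears in the visible SAP.

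**The concern.** When randomisation is stratified on factors that predict outcome, the arms are balanced on them by design. A model without those factors leaves their variance in the residual. Its standard errors then describe a less controlled design than the one that was run, so intervals come out too wide and between-arm tests are conservative. The protocol does carry the strata into its tests for binary endpoints, but not into its models for continuous ones. With those tests absent from the visible SAP, no visible SAP efficacy analysis uses the stratification factors.

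What is at stake is the width of the reported Week 12 intervals, plus one point on which the two documents differ for four secondary endpoints.

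**Working it through.** **1. The plan's own figures reproduce.** Inputs from SAP 7.2: mean change 3, SD 2.3, 37 evaluable (high, mid) or 18 (low), two-sided 5%. Half-width = t(0.975, n−1) × 2.3/√n = 0.767 (n=37) and 1.144 (n=18), matching the stated 0.77 and 1.14. One-sample t power from the noncentral t is above 0.9999 (n=37) and 0.9994 (n=18), so the claim of more than 90% holds with a wide margin.

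**2. Reported standard error with the strata added.** The documents do not say how much variance sex and BMI explain, so R² = 2%, 5% and 10% of residual variance are assumed. Also assumed: 37/37/18/37 evaluable (37 for pregabalin is my figure), so N = 129; SD 2.3 as the residual SD before strata; and one variance pooled over arms, since SAP 9.3.1.2 gives no arm-specific covariance. Week 12 is treated as an ANCOVA with 124 residual degrees of freedom, or 122 with two more parameters.

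- Ratio of reported SEs = √(1−R²) = 0.990, 0.975, 0.949, a fall of 1.0%, 2.5%, 5.1%.
- Half-width without strata = t(0.975, 124) × 2.3/√n = 0.748 (n=37) and 1.073 (n=18).
- Half-width with strata = t(0.975, 122) × 2.3 × √(1−R²)/√n, shown in the table.

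**3. The same for the stated estimand.** SAP 9.3.1.1 targets the mean in the population set by the eligibility criteria. For that target the sex and BMI mix of the sample is itself random, and the variance is about SD² × [(1−R²)/n + R²/N]. Relative to SD²/n, the SE ratio is √(1 − R² + R²n/N). For n=37 and R² = 10%: √(0.90 + 0.10 × 37/129) = √0.9287 = 0.964, a fall of 3.6%.

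| R² | SE fall, margins fixed | Half-width, n=37 / n=18 | SE fall, margins sampled, n=37 | Half-width, n=37 |
|---|---|---|---|---|
| 2% | 1.0% | 0.741 / 1.062 | 0.7% | 0.743 |
| 5% | 2.5% | 0.730 / 1.046 | 1.8% | 0.735 |
| 10% | 5.1% | 0.710 / 1.018 | 3.6% | 0.721 |

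**4. What the estimate itself gains.** Simulation: Week 12 ANCOVA, 175 subjects randomised 2:2:1:2 in blocks within the four strata, sex and BMI each 50/50, about 26% random dropout, R² = 10%, 20,000 runs.

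- High dose: mean reported SE falls from 0.379 to 0.360 (about 5%). The true SD of the estimate falls only from 0.369 to 0.365 (about 1.1%). Coverage of the 95% interval moves from 95.8% to 94.8%.
- Low dose: the true SD falls from 0.522 to 0.516 (about 1.1%), and coverage moves from 95.6% to 94.7%.

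A separate 4,000-run simulation of the same kind gave a fall of about 0.6% in the true SD (high dose) and coverage moving from 96.0% to 94.8%.

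**5. If the strata explain nothing.** In a simulation without stratified allocation, the two extra parameters raise the SE by 0.6% (high, mid) to 0.7% (low).

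**6. A between-arm contrast, if one were reported.** With balanced strata, the actual size of a nominal 5% test that ignores them is about 2 × [1 − Φ(1.96/√(1−R²))] = 4.8%, 4.4%, 3.9%.

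**The case against.** The strongest reply is that this is a preference. Both documents specify the same model, the primary test is within-group with power above 99.9%, and no between-arm contrast is visible in the model text. The usual reason for modelling strata is therefore largely absent. The 5% fall in reported SE also overstates the benefit. Because stratification already balances the arms, the adjusted and unadjusted arm means are nearly the same number. The change mostly removes a slight conservatism, and it leaves a reported SE that is slightly small for the population mean because it treats the stratum margins as fixed.

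All of that stands, and it sets the size of the point. It does not remove it: the present intervals are slightly wider than the design warrants if the strata matter, and the correction costs almost nothing.

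A reader might infer two stronger things. One is that omitting the strata invalidates the primary analysis or departs from the protocol. It does neither. The other is that the SAP dropped the Cochran-Mantel-Haenszel tests without justification. The documents do not support that. Protocol 12.3.3 defers analysis details to the SAP, and the SAP wording is unambiguous. Protocol 12.3.3.2 names no arms to compare. The SAP contents list also has redacted entries, so a recorded reason may exist out of sight.

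**Conclusion.** The omission is real and small. It is a missed improvement on which protocol and SAP agree, and it affects neither the validity of the within-group test nor the stated power. If sex and BMI explain 2%, 5% or 10% of residual variance (assumed), reported SEs would fall by about 1%, 2.5% or 5%. For the population estimand the corresponding figures are about 0.7%, 1.8% and 3.6% at n=37, so the half-width at 10% is nearer 0.721 than 0.710. The true precision of each arm mean improves by about 1% or less. The practical gain is coverage close to the nominal 95% in place of about 96% at R² = 10%, and a size near 5% in place of about 4% for any between-arm contrast.

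The mismatch over the Cochran-Mantel-Haenszel tests is genuine between the protocol and the visible SAP, but it is a documentation item covering four secondary endpoints. It does not carry the point.

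**What to change.** **Main change.** Before database lock, add sex and BMI category, as randomised, as fixed main effects to the NPRS model (SAP 9.3.1.2) and the DSIS model (SAP 9.3.2). Put matching wording in Protocol 12.3.3.1 and the synopsis. State that least squares means are taken at the observed Full Analysis Set margins.

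**Cost.** Two parameters per model and a SAP amendment, for which SAP 4 already provides. Both variables are collected for randomisation and tabulated under SAP 9.2.2. The downsides are an SE increase of up to about 0.7% if the strata explain nothing, and the slightly small SE for the population mean noted above.

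Main effects assume the same stratum effect in every week. If the effect grew linearly to Week 12, they would still cut the reported SE by about 0.8%, 2.0% or 4.3% at the three R² values. Crossing both factors with 12 weeks would take 2 × 12 = 24 parameters and add only about 0.2, 0.5 or 1.1 percentage points, so I would not do it.

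**Companion item.** Reconcile Protocol 12.3.3.2 with SAP 9.3.2 in one of two ways:

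- Keep the stratified test in the SAP, name the arms compared, and label it exploratory, since between-arm comparisons are unpowered and multiplicity is not adjusted. Cells would be thin: if evenly spread, 25/4 ≈ 6 low-dose and 50/4 = 12.5 other-arm subjects per sex-by-BMI cell.
- Align the protocol with the descriptive plan and record the reason, if redacted text does not already do so.

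Either is a short wording change, plus one exploratory table if the test is kept.

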## **7.2              Sample Size and Power**

The sample size is based on the primary analysis of the primary endpoint. With 37 evaluable subjects in the VX-548 high or mid dose group and 18 evaluable subjects in the VX-548 low dose group, there is more than 90% power in any VX-548 dose group to detect a mean change from baseline of 3 with a single group *t*-test at the 2-sided 0.05 significance level, assuming the SD is 2.3. With an evaluable sample size of 37, a 2-sided 95% CI for the mean change from baseline in the high or mid dose group will extend 0.77 on either side of the observed mean, assuming the CI is based on the *t*-statistic and the observed SD is 2.3. Under the same assumptions and an evaluable sample size of 18, a 2-sided 95% CI for the mean change from baseline in the low dose group will extend 1.14 on either side of the observed mean. To account for a 25% dropout rate, 50 subjects each will be enrolled in the VX-548 high dose, VX-548 mid dose, and the pregabalin groups; 25 subjects will be enrolled in the VX-548 low dose group. The total sample size is approximately 175 subjects.

The study is not powered for comparison between the VX-548 doses and the pregabalin reference arm.

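### If the unstructured MMRM fails to converge, the only fallback is compound symmetry with a single variance, which misstates the Week 12 confidence interval whenever the variance changes over the weeks

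*SAP*

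**What the plan says.** SAP 9.3.1.2 fits the change in weekly average NPRS at Weeks 1 to 12 by restricted maximum likelihood, with treatment, week, baseline and their interactions with week as fixed effects. On the covariance it says "An unstructured co(variance) structure will be used to model the within-subject errors", followed by the single contingency "If there is a convergence issue, then a compound symmetric covariance matrix will be used to model the within-subject errors". Kenward-Roger is the only method named for degrees of freedom and standard errors. The reported result is the Week 12 LS mean change, which "for each treatment group will be presented with the corresponding SE, 95% CI and P-value".

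Protocol 12.3.3.1 lists the fixed effects but no covariance structure, so it supplies no other fallback.

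Under SAP 9.3.2 the DSIS change "will be analyzed similarly to the primary analysis as specified in Section 9.3.1.2", so it inherits the rule. There, "the LS mean change from baseline at each week will also be presented together with the corresponding SE and 95% CI by treatment group", and a figure shows the weekly means with their SEs.

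**The concern.** Twelve weekly values give 12 × 13 / 2 = 78 covariance parameters in the unstructured matrix. Compound symmetry has two: one variance and one correlation. The SAP does not use the word homogeneous, but compound symmetry without qualification means a common variance. The plan therefore drops from 78 parameters to 2 with nothing in between.

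If the fallback is used and the variance of change differs by week, the Week 12 standard error is built on the wrong variance. Kenward-Roger corrects for small samples while taking the stated structure as true, and no empirical standard error is specified.

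Precision is the more informative output here. The primary analysis is within-group, a test against zero is almost sure to succeed under the planning assumptions, and SAP 7.2 says the study is not powered against pregabalin. SAP 7.2 also describes the sample size through the interval: with 37 evaluable subjects it "will extend 0.77 on either side of the observed mean". For DSIS, any trend in variance would make some weekly intervals too narrow and others too wide.

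**Working it through.** **Inputs.** From SAP 7.2: SD of change 2.3, mean change 3, 37 evaluable subjects (high or mid dose) and 18 (low dose), two-sided 5%, 25% dropout. From SAP 7.1: arms of 50, 50, 25 and 50. From SAP 9.3.1.2 and Appendix A: 12 weekly averages. The documents give no SD by week and no between-week correlation.

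**Step 1: the plan's own figures.** Half-width = t(0.975, n−1) × SD / √n.
- n=37: 0.767, matching the stated 0.77.
- n=18: 1.144, matching the stated 1.14.

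The test statistic at the planned effect is 3 / (2.3/√37) = 7.93 and 3 / (2.3/√18) = 5.53. One-sample power exceeds 99.9% in both cases.

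**Step 2: effect of one common variance, complete data.** Compound symmetry estimates one variance, the mean of the 12 weekly variances. So

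reported SE / true SE at Week 12 = √(mean of SD²) / 2.3,

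and coverage ≈ 2Φ(1.96 × ratio) − 1. The half-widths below are the planned ones multiplied by the ratio. The assumption is that the SD, taken as the model's residual SD, moves linearly from its Week 1 value to 2.3 at Week 12.

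| Week 1 SD | Common SD | SE ratio, Week 12 | Half-width n=37 | Half-width n=18 | Coverage |
|---|---|---|---|---|---|
| 1.2 | 1.784 | 0.776 | 0.60 | 0.89 | about 87% |
| 1.7 | 2.009 | 0.873 | 0.67 | 1.00 | 91.3% |
| 2.0 | 2.152 | 0.936 | 0.72 | 1.07 | 93.3% |
| 2.3 | 2.300 | 1.000 | 0.77 | 1.14 | 95.0% |
| 2.6 | 2.452 | 1.066 | 0.82 | 1.22 | 96.3% |

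Example, Week 1 SD 1.7: √(mean of SD²) = 2.009; 2.009 / 2.3 = 0.873; 0.767 × 0.873 = 0.67.

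**Step 3: the early weeks.** The Week 1 SE ratio is the common SD over the Week 1 SD: 2.152/2.0 = 1.08, 2.009/1.7 = 1.18, 1.784/1.2 = 1.49. In the rising cases the Week 1 interval is too wide while the Week 12 interval is too narrow. This bears on the weekly DSIS display. The NPRS SD is borrowed for it, because no DSIS SD is given.

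**Step 4: with dropout.** Simulation of the SAP's fixed effects under REML compound symmetry, arms 50/50/25/50, 25% random monotone dropout, normal data, true correlation exchangeable 0.7 or AR 0.9, 1,000 runs per case, high- and low-dose arms. Model-based SEs with 150 df stood in for Kenward-Roger.

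| Week 1 SD | SE ratio | Coverage |
|---|---|---|
| 1.2 | 0.72–0.78 | 84–87% |
| 1.7 | 0.81–0.86 | 89–91% |
| 2.0 | 0.88–0.95 | 92–94% |
| 2.3 | 0.94–1.03 | 94–97% |
| 2.6 | 0.97–1.11 | 94–97% |

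A second, separately coded simulation (400 runs per case, AR 0.93 in place of 0.9, 170 df) gave coverage of 83.5–87.0% from 1.2, 88.8–93.5% from 1.8, 93.2–94.8% when constant and 96.0–98.8% when falling from 3.0.

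**Step 5: the alternatives.** With Week 1 SD of 1.2 or 1.7, both correlations and both arms, 300 runs per case:
- compound symmetry as written: 81–92%;
- heterogeneous compound symmetry: 92–97%;
- heterogeneous AR(1): 94–97%;
- compound symmetry with Mancl-DeRouen SE and n−1 df: 95–98%;
- uncorrected sandwich, low-dose arm: 91–95%.

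Heterogeneous Toeplitz was not simulated.

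**The case against.** The strongest objection is that the fallback will probably not be needed. The unstructured matrix is pooled over all four arms, so about 175 × 0.75 = 131 subjects would have Week 12 data, which is ample for 78 parameters. In a trial of the planned unstructured model on simulated data (random dropout, some cases with 5% intermittent missing weeks, poor starting values), all 200 of 200 fits converged. That was not SAS and real diary data are less tidy, so failure is not excluded, but this point stands: the trigger is unlikely.

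It also stands that the direction is unknown, that every magnitude rests on an assumed SD path, and that 87% coverage needs a Week 12 SD almost twice the Week 1 SD. Significance against zero hardly changes, and this is a Phase 2 study without multiplicity control. The SAP does prespecify a deterministic fallback, so nothing is contradictory or missing. A single clause naming heterogeneous compound symmetry would remove most of the problem. Finally, the SAP contents page has a blacked-out entry between 9.3.2 and 9.3.4, so supportive analyses may exist unseen, though a fallback for the primary model belongs in 9.3.1.2.

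None of this defends a common variance once the fallback is in use. The points limit how often the harm arises and how large it is. They do not make the rule a good one, and replacing it after seeing the data would be a post hoc choice.

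**Conclusion.** The concern holds. If the unstructured fit fails and the variance of change differs by week, the prescribed fallback misstates the Week 12 SE and interval, and nothing else in the visible plan guards against it. For a Week 1 SD between 2.0 and 1.2 rising linearly to 2.3, the interval is about 6% to 22% too narrow with complete data (1 − 0.936 and 1 − 0.776), with coverage of about 93% down to 87%. With 25% dropout, simulated coverage is 92–94% down to about 84–87%. With constant SD the interval is about right; with falling SD it is about right or too wide.

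These figures depend on assumed SD paths, normal data and random dropout. The harm is to reported precision, not to the test against zero, and no probability of non-convergence is known. The change should be made because it is cheap and this is the only rule for failure of the primary model. Confidence is medium.

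**What to change.** Replace the fallback sentence in SAP 9.3.1.2 with an ordered rule, taking the first step that converges:

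1. the unstructured matrix with new starting values or another optimisation algorithm;
2. heterogeneous Toeplitz;
3. heterogeneous AR(1);
4. heterogeneous compound symmetry;
5. homogeneous compound symmetry as a last resort, with the Mancl-DeRouen bias-corrected sandwich SE and a t reference with df equal to the arm's number of subjects with a Week 12 value, minus 1.

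Keep Kenward-Roger for steps 1 to 4. State in the report which step was used. Apply the same rule to DSIS in SAP 9.3.2; if step 5 is reached, take the df at other weeks from that week's count.

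The cost is one paragraph and a little programming, and nothing changes if the planned model converges. SEs would be slightly noisier at step 5. The sandwich repairs the SE only: it does not remove bias in the estimate if dropout depends on earlier scores and the working structure is wrong.
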